**CRP polymorphisms.** Two SNPs occur in the CRP gene (641G□C and 1846G□A) that are independently associated with circulating CRP levels. Both SNPs will be characterized through RFLP assays as recently published [331]. Briefly, for the 641G□C SNP, a 279 bp amplicon will be amplified from 50 ng genomic DNA using the sense primer (5' TCAGGGATCGTGGAGTTC) and antisense primer (5' GCCTTGCACCTCATACTTC). This fragment contains a restriction site for *Tsp*451 which involves the 641G□C polymorphic residue such that restriction digestion with this enzyme yields restriction fragments of 90 bp and 189 bp for the wildtype 641G allele while leaving the 641C variant allele uncut. For the 1846G□A SNP, a 227 bp amplicon will be amplified from 50 ng genomic DNA using the sense primer (5' GGAGTGAGACATCTTCTT) and the antisense primer (5' CTTATAGACCTGGGCAGT). The 227 bp fragment contains a *Hpy*CH4III restriction site involving the 1846G□A polymorphic residue such that the wildtype 1846G is cut to yield 97 bp and 113 bp fragments, while the 1846A variant is uncut. Both RFLP reactions will be analysed in 3% agarose gels, and the bands will be visualized by UV light following ethidium bromide staining.

**IL-6 polymorphism.** A SNP occurs at -174G□C in the promoter region of the IL-6 gene. The presence of the G allele induces higher constitutive IL-6 expression levels, and higher levels after LPS or IL-1 mediated induction, relative to the C allele [332]. This SNP will be identified by first amplifying 50 ng genomic DNA using a sense primer from -332 to -312 (5' CTTCGTGCATGACTTCAGCTT) and an antisense primer from -80 to -101 (5' GATAAATCTTGTTGGAGGGTG). The resulting 253 bp fragment will be treated with *Exo1* and alkaline phosphatase, and then cycle-extended one ddNTP using a 23 base sense SNaP primer (5' TTTTCCCCTAGTTGTCTTGC) that abuts the -174G□C polymorphism, and incorporation of a ddGTP or ddCTP will be determined by analysis on an ABI Prism 3730 DNA analyzer. The G allele showed roughly four times greater expression of IL-6 than the C allele in lymphocytes stimulated by liposaccharide or IL-1 [332]. In a subset of 102 subjects, GG homozygotes had twice the level of fasting plasma IL-6 than CC homozygotes. (p<.02) [332].

**Flow Cytometry.** Using separated PBMCs, 0.5 – 1x 10^6 cells will be aliquoted into tubes. The cells will be incubated with each mAb and then washed and resuspended with 2% Formalin solution and stored at 4C until analyzed with a BD FACSCalibur flow cytometer. We will measure the percentage and absolute number of leukocyte activation markers CD11A, CD11B, CD62L, CD14, sCD14, and CD66B [333].

**Adhesion Molecules.** We will assess sICAM-1, sVCAM-1 and E-selectin, as well as serum amyloid A (SAA), a family of apolipoproteins associated with HDL in plasma.

**Gene Expression Studies Using Focused Microarrays.** These experiments are designed to detect and quantify gene expression for inflammatory cytokines, stress and appetite hormones, chemokines, growth factors and accessory molecules that are produced in the subjects. Peripheral blood leukocytes (PBLs) will be obtained at each time point and used for molecular studies. Purified RNA prepared from the PBLs will be used to do gene expression using focused microarrays.

The following oligo arrays will be used to characterize gene expression in peripheral blood mononuclear cells (PBMCs): **Array 1) Inflammatory Cytokines & Receptors.** This array profiles the expression of 113 key genes involved in the inflammatory response. The chemokines, interleukins, and TNF ligands involved in the inflammatory response are represented as well as their receptors. **Array 2) T-cell and B-cell Activation.** This array profiles 113 genes representing T-cell and B-cell activation, which are both key parts of adaptive immunity. This array includes most of the genes known to influence the maturation of the B and T cell response and many of these 'activating' genes are produced by the macrophage or dendritic cells. **Array 3) NF $\kappa$ B Signaling Pathway.** This array profiles the expression of 113 genes related to NF $\kappa$ B-mediated signal transduction. The

array includes genes that encode members of the Rel, NFkB, and I kB families, NFkB-responsive genes, extracellular ligands and receptors that activate the pathway, and kinases and transcription factors that propagate the signal. We may also explore use of focused microarrays for expression of stress and appetite hormones, as well as obesity-related genes, because they may play a role in the strength of the immune system's proinflammatory cytokine responses to stress, as well as dietary challenges [334]. New nutrigenomics research involves a study of gene expression in response to changing conditions such as nutritional intervention studies to better understand the effects of diet on gene expression [335]. For example, one study showed a decrease in oxidative stress and inflammation genes in response to a low-calorie diet [335]. Approximately  $1 \times 10^6$  PBMCs (1-2ml heparinized whole blood) will be used for each array.

Note that we are not proposing to provide feedback to participants about the results of genetic testing. We carefully considered the issue of whether we should provide feedback on the results of their cytokine genotype profile, and decided that we would not, based on several factors. First, the health relevance of the cytokine/CRP polymorphisms is still a matter of considerable debate in the literature; for instance, though most studies of the IL-6 G174C polymorphism indicate that the 174G allele is associated with increased IL-6 levels and is a risk factor for various diseases, two studies oppositely state that it is the 174C allele that is associated with high levels, and three studies indicate that the C allele is the disease risk factor; indeed, our own data from older adults also show contrary results. Furthermore, there might be both an age and sex effect on these associations, although there is even some contradiction as to the specifics in these studies. As for TNF- $\alpha$ , there are also many pathologies involving TNF- $\alpha$  that do not associate with the 308 polymorphism (eg., rheumatoid arthritis), and at least one study that states that this polymorphism doesn't affect levels [336]. Thus, it would be premature to provide feedback to the study participants when the actual impact of the polymorphisms is still unclear. Similarly, the same considerations apply for the microarray studies; these are very preliminary studies in new areas that involve small samples, and any results would be extremely preliminary and in need of replication. Accordingly, our consent form states that we will not provide feedback.

**Glucose:** The CRC uses Immobilized Enzyme Technology using the YSI 2300 Stat Plus Glucose and Lactate Analyzer from YSI International, Yellow Springs, Oh. Assay coefficient variation is 2% with calibration occurring every 15 minutes. The sensitivity of this instrument is 2.5 mg/dl.

**Insulin:** Chemiluminescence methodology using the Immulite 1000 (Siemens Medical Solutions Diagnostics) Sensitivity for this assay is  $2 \mu\text{IU}/\text{ml}$ . Intra-assay coefficient of variation is 5.7% and Inter-assay coefficient variation is 6.7%. Insulin resistance (IR) will be determined from fasting serum insulin and glucose measures as indexed by the Homeostasis Model Assessment (HOMA) [337, 338]. Saturated fat worsens insulin sensitivity and adversely effects glucose metabolism [339].

**Fatty acid composition of red blood cells.** Omega-3 enhances triglyceride clearance following high-fat meals [340], and better triglyceride clearance is related to lower postprandial inflammation, but relationships between dietary omega-3 and postprandial inflammation have not been studied. The fatty acid composition of red blood cells drawn as part of the fasting blood sample will provide data on habitual fatty acid intake [341], assayed as described previously [342].

**Endocrine Data.** Stressors can substantially elevate epinephrine and norepinephrine, as well as other stress hormones [343-346]. The ability to "unwind" after stressful encounters, i.e., quicker return to one's neuroendocrine baseline, influences the total burden that stressors place on an individual [347]. Catecholamine samples will be collected at set intervals during the protocol if we have sufficient resources. Serial blood samples will be obtained at the OSU CRC. Plasma catecholamines will be assayed using HPLC with ElectroChemical Detection using standards and chemicals (Alumina extraction) purchased from ChromSystems (Munich, Germany, U.S. affiliate Thermo-Alko). C-18 Columns (Waters), an HPLC pump and detector (ESA), and a 717-plus Autosampler (Waters Corporation) are the configuration that will be utilized for these determinations. The intra-assay coefficient variation for norepinephrine is 3% and the inter-assay coefficient variation is 6%. The intra-assay coefficient variation for epinephrine is 6% and inter-assay coefficient variation is 13%. Sensitivity for norepinephrine is 15 pg/ml and 6 pg/ml for epinephrine.

Related to our immunological focus on changes in inflammatory cytokines, we also hope to assay leptin, ghrelin, and adiponectin, depending on available funds. Higher concentrations of plasma adiponectin are associated with lower waist-hip ratios, lower insulin resistance, lower diastolic pressure, lower triglyceride concentrations, and lower TNF- $\alpha$  receptor concentrations [348].

Glucocorticoids and insulin work together in the regulation of serum leptin; increases in leptin from the lowest to highest point daily are related to insulin changes induced by meals [349]. Sufficient endogenous

cortisol secretion is important for insulin's effects on leptin production [349]. However, leptin-resistant obesity may eventually be caused by leptin stimulation related to glucocorticoids [349].

Leptin, ghrelin, and ghrelin (total) will be assayed by the CRC using the respective RIA kits (Millipore Corporation, St. Charles, MO 63304). For leptin, the intra-assay coefficient of variation is 4.2% and inter-assay coefficient of variation is 4.5%; sensitivity is 0.5 ng/ml. For adiponectin, the intra-assay coefficient of variation is 3.8% and inter-assay coefficient of variation is 8.5%; sensitivity is 1 ng/ml. For ghrelin, the intra-assay coefficient of variation is 6.4% and inter-assay coefficient of variation is 16.3%; sensitivity is .09 ng/ml.

Saliva will be collected for cortisol assay 15-18 times during each visit using a salivette (Sarstedt, Newton, North Carolina), an untreated sterile cotton roll placed in the subject's mouth for ~2 minutes to ensure saturation. Each subject's saliva samples will be frozen after collection and analyzed by the CRC within the same assay using the Cortisol Coat-A-Count RIA (Siemens Medical Solutions Diagnostics, Los Angeles); the intra-assay coefficient of variation is 4.3%, the inter-assay coefficient of variation is 5.2%, and sensitivity is .025 ug/dl.

Salivary  $\alpha$ -amylase will be assayed from saliva to provide a marker for the activity of the sympathetic nervous system[350]. Amylase has also been directly associated with ratings of satiety and fullness, and inversely associated with hunger and desire to eat. It will be measured by the CRC lab using an enzyme kinetic assay.

**Specimen Storage and Protection:** Specimens will be stored in a -80° freezer that is located at the Institute for Behavioral Medicine Research. All laboratory samples have only the study's identifying number and date and sample number, and individuals in the lab only have access to those parts of the data that are necessary to their particular job.

## F. Human Subject Information

**Potential Risks:** The study has only modest risks associated with the procedures. Personal questions contained in questionnaires and interviews and cognitive tests may make participants uncomfortable or could produce stress. The blood draws and the catheter put subjects at small risk for pain, infection, a bruise at the draw site, or fainting. There is a minor risk of an allergic response to the tape used to hold the catheter in place that may include redness or a rash, swelling, small blisters, itching, and discomfort on the arm where the skin was covered by the tape. A single DXA scan produces a very small amount of radiation, approximately 1/10th of that experienced during a cross-country air flight or 1/120th of what participants would experience during a dental scan. For the cold pressor test, the primary risk is transient pain/discomfort related to the water temperature, no other known risks are associated with this procedure. For the cardiac stress testing, risks may include feeling fatigued after the testing and/or shortness of breath, as well as transient muscle soreness. The discomforts and/or risks associated with a maximal exercise test are comparable to those encountered during any strenuous athletic event and include occasional disorders of heartbeat, abnormal blood pressure, and a very remote chance of heart attack. For the typhoid vaccine: The Vi polysaccharide typhoid fever vaccine is commonly administered when people travel to areas where typhoid fever is endemic; the vaccine is well-tolerated in adults [351, 352]. The safety profile for the typhoid vaccine is well-established, and is supported by over 20 years of immunogenicity trials, efficacy trials, and post-marketing surveillance data [352]. For example, out of more than 22 million doses of the Vi vaccine that were distributed between 1986 and 1996, only 140 nonserious adverse events and 20 serious adverse events were reported [351]. Side effects are typically mild and infrequent [351, 353], occurring in less than 10% of all adults [352]. The most common side effects are local pain, redness, induration, or swelling at the injection site [170]. A small subset of people who receive the vaccine report feeling feverish; in two studies comparing Vi vaccine to placebo, feverish feelings, malaise, and headache were reported about 10% more often in those who received the typhoid vaccine [352]. However, objectively confirmed fever is uncommon, occurring in less than 1% of subjects after a 25- $\mu$ g dose [352]. Furthermore, in a study of 104 Vi vaccinated participants, none required time off of work or any form of medical treatment as a result of the vaccine [351]. Other systemic reactions such as skin disorders (including rash), muscle or joint pain, or gastrointestinal complaints are rare, and occur in less than 2% of individuals who receive the vaccine [170, 352].

**Protection Against Risks:** The following steps will be taken to protect against risks.

Recruitment and Informed Consent. Written informed consent will be obtained at the beginning of the screening session. The consent form will be posted on the web along with the study description at the recruitment web site, so the participants have the opportunity to read the form carefully prior to applying for participation. In addition, once a participant has been scheduled for screening, they will receive a copy of the

informed consent form, the HIPAA form, and the Notice of Privacy Practices along with the letter confirming their appointment date/time. On arrival in the CRC for their screening appointment, the key points of the study will be reviewed and they will be asked to sign the informed consent prior to any other activities.

Confidentiality. The risk of breaching confidentiality is low. All data are coded by subject number, and questionnaires do not include names or other identifying information. All laboratory samples have only the study's identifying number and date and sample number. Identifiers are stored on an Access database that is separated from the remainder of the data, and individuals in the lab only have access to those parts of the data that are necessary for their particular job. Data will only be reported as averages, with no identifying individual data.

For questionnaires and interviews. As an additional precaution, as part of the packet given to individuals at their first session, along with a copy of the informed consent, we will give all subjects a list of mental health agencies when they are finished with their initial appointment on the project. Note that the consent form also informs participants that we will contact appropriate authorities if the participant appears to be at imminent risk for harm to herself or others. Suicide risk is assessed in the SCID interview, and if the subject endorses suicidality, we have a protocol in place that will be activated. The protocol includes notifying CRC staff, assessment by clinically trained personnel, and/or notifying authorities as appropriate.

For blood draws and the catheter. Blood draws and catheter insertions will be conducted by experienced nurses in the Clinical Research Center to minimize the risks associated with these procedures.

Discovery of a previously unknown condition. Any potentially abnormal results from the hospital lab data will be first discussed with [name], the physician on the study, to confirm the nature and seriousness of the problem; if there appears to be reason for concern, participants would be informed of the abnormal value and advised to seek treatment from their personal physician.

DXA scan. A single DXA scan produces a very small amount of radiation, approximately 1/10th of that experienced during a cross-country air flight or 1/120th of what participants would experience during a dental scan.

For the typhoid vaccine. Consistent with any vaccine procedure, we will exclude individuals who have a severe allergy to any component of the vaccine. In addition, our study will exclude subjects who are currently ill or immunocompromised. Vaccinations will be conducted by experienced nurses in the Clinical Research Center to minimize the risks associated with these procedures. Side effects will be carefully monitored in the CRC for 7.5 hours after vaccine administration.

Exercise testing. The risks of serious injury during exercise testing in healthy subjects are negligible. Even in populations with chest pain or established coronary artery disease, fatal arrhythmias or myocardial infarction occur in less than 1 of 10,000 exercise tests. There is no alternative to the exercise stress testing; stress testing is the gold standard for evaluating cardiopulmonary endurance. All participants will be carefully screened and those with serious medical conditions will not be eligible for participation. In addition, we will conduct all exercise testing studies in the CRC under the supervision of an exercise physiologist and a physician, and emergency coverage is readily available.

For blood draws and the catheter. Blood draws and catheter insertion will be conducted in the General Clinical Research Center to minimize the risks associated with these procedures.

For the cold pressor test. Participant will be informed that they may remove their foot from the cold water when the pain or discomfort becomes too great. The procedure lasts 5 minutes, not long enough for any lasting effects due to the water temperature.

**Benefits:** Participants will receive a report based on their answers to the food recall interviews. The report will tell them about their eating patterns, such as how closely their number of servings in each food group consumed daily matches USDA recommendations. In addition, this report will show your average daily intake of different nutrients and recommendations for improving your diet. Participants will also receive the results of their exercise test. The results obtained from the exercise test will provide them with information about their physical fitness, cardiorespiratory endurance, and ability to sustain prolonged exercise related to others in their age group.

**Compensation for time:** The total protocol will take 23-24 hours, and participants will receive up to \$600 for participation in the full study.

**Reporting of Adverse Events:** Reporting of adverse events will occur as detailed in the Data Safety Monitoring Plan listed below.

**Premature Removal of Participant:** Study participants who conclude their participation either prematurely or at full completion, and who have an unresolved adverse event will be followed by telephone by a member of the study team until the event(s) is (are) resolved.

**Study Termination Procedures:** It is not anticipated that the study will (need to) be terminated prematurely, either due to acceptance of the null hypothesis and/or adverse events, or other, and that subjects' safety will not be compromised.

Annual data checks will assess significance and effect sizes for key areas; if we unexpectedly found that none of these was significant or could be significant given the planned sample size, then we would stop the trial.

## G. Statistical Methods

### Power and Sample Size

**NOTE: our projected sample for the two CRC admissions is 180, reflected in the sample size calculations below which are based on typhoid vaccine administration. The protocol describes a sample of 240 because any screening participants who are ineligible and/or who elect not to continue are counted in the total by the IRB.**

Power calculations were based on previously published data estimating the effect of typhoid vaccine on inflammation (IL-6) and mood. Wright [56] evaluated both proinflammatory cytokine responses and mood following injection of typhoid vaccine or placebo in 30 healthy male volunteers. The effect of vaccine on IL-6 was large; at 3h the mean IL-6 in the vaccine group was 1.59 (SD=0.81) compared to 0.53 (SD=0.30) in the placebo group, yielding an effect size of Cohen's  $d = 1.5$ . The effect of vaccine on negative mood was also large, though smaller than the effect on inflammation. At 3h post-injection the mean negative mood was 12.8 (SD=7.7) in the vaccine group compared to 7.4 (SD=5.8) in the placebo group, yielding an effect size of  $d = 0.76$ . Based on these results, we expect the effect of vaccine on mood to be smaller than the effect on IL-6, thus power calculations were designed to ensure adequate sample size to detect effects of vaccine on mood, which will ensure adequate power for IL-6 as well.

The three specific aims for the proposed study are to evaluate (1) the effect of cardiorespiratory fitness on vaccine response, (2) the effect of age and depressive symptoms on vaccine response, and (3) the moderating effect of fitness on the age- and depression-related effects on vaccine response. Since each woman will serve as her own control by receiving both the vaccine and the placebo injection, the corresponding hypotheses all involve complex interactions: (1) the two-way interaction between fitness and injection type (vaccine/placebo), (2) the two-way interaction between age/depression and injection type, and (3) the three-way interaction of fitness by age/depression by injection type. Sample size requirements are considerably higher for testing higher-order interaction terms, thus we based required sample size on the tests of the third specific aim: the three-way interaction between fitness, age/depression, and injection type, while ensuring adequate power for the first two aims as well. Throughout we assumed 2-tailed tests with an 0.05 level of significance and used SAS PROC GLMPOWER for calculations.

Data from Wright [56] gives us an estimate of the overall (averaged across fitness and age/depression) effect of vaccine and placebo on negative mood: at 3h post-injection the mean in their study was 12.8 (SD=7.7) for vaccine and 7.4 (SD=5.8). We anticipate larger effects in our sample as we are recruiting older subjects who are breast cancer survivors, thus we assume that average negative mood responses to both the vaccine and placebo will be 20% higher in our sample of older breast cancer survivors. In order to calculate required sample size for the three-way interaction, we hypothesized the mean negative mood post-vaccine and also post-placebo for each of four groups: (a) high fitness/low depression, (b) high fitness/high depression, (c) low fitness/low depression, (d) low fitness/high depression. We hypothesized that the highest negative mood post-injection (either type) would be in group (d) low fitness/high depression, and the lowest negative mood would be in group (a) high fitness/low depression. Additionally we hypothesized that the average effect of depression on mood would be larger than the effect of fitness on mood and (as in Hypothesis 3) the effect of depression among women with high fitness would be smaller than the effect of depression among women with low fitness. The hypothesized means are shown in the **Table** below. We note that even the largest hypothesized mean is only approximately 1.25 SD above the estimated overall mean and the smallest is only  $\frac{3}{4}$  SD below this mean, thus these estimates seem reasonable.

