## A.2 Typhoid Vaccine as a Peripheral Immune Stimulus

A number of studies have used typhoid vaccine to induce transient systemic inflammation [48-60]. In studies with healthy young unmedicated subjects, the maximum cytokine increases occurred 2-4 hours post-vaccination, with a 4-6 fold increase in IL-6 and up to a 30-fold increase in IL-1Ra [49, 54].

In contrast, older subjects show greater reactivity and slower recovery. For example, subjects whose average age was 58 had a 10-fold rise in IL-6 post-vaccination [60]. Moreover, among people who were around 59 years old, IL-6 was higher at 8 hours than at 4 [59]. Although subjects in their early twenties did not show significant heart rate changes, vaccination increased heart rate by 5 beats per minute in men and women whose average age was 41.5 [52]. Thus, consistent with the endotoxin studies, older participants' typhoid vaccine responses were larger in both magnitude and duration compared to younger individuals.

We anticipate that inflammatory responses to typhoid vaccine will be variable, and this variability will provide important information about psychological and biological vulnerabilities. For example, young men who had larger IL-6 responses to typhoid vaccine also had larger increases in fatigue, negative mood, systolic blood pressure, and salivary 3-methoxy-phenylglycol, a major norepinephrine metabolite, in response to a laboratory stressor [48]. Our design will allow us to assess how inflammatory responsiveness and associated symptoms differ following vaccination among breast cancer survivors who are likely to have heightened post-treatment inflammation as suggested by our data described in Preliminary Results. In this vulnerable group, the ability to minimize inflammatory responsiveness is particularly important.

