## METHODS

### B. Participant selection

**Participants:** A total of 240 women ages 45-65 who have been diagnosed with stage I-IIIA breast cancer will be recruited 1-8 years after the completion of all primary cancer treatment except for longer-term hormonal therapies (tamoxifen, aromatase inhibitors). We will recruit women who have received one of the two most common stage I-IIIA chemotherapy regimens, either docetaxel/cyclophosphamide or doxorubicin/cyclophosphamide followed by paclitaxel to provide uniformity of prior treatment. All women will be postmenopausal, defined as having FSH and estradiol within the institutional postmenopausal range at the time of study entry and no menstrual cycle in the last 12 months.

Cardiorespiratory fitness is a key variable, and it is thus important to select women who represent the full range of fitness. We anticipate that recruiting women at the lower end of fitness will not be a problem, but may represent a greater challenge in recruiting the most fit women. We will screen women prior to any in-person appointments using the CHAMPS [152-155] to maximize selection of more active women, particularly at higher BMIs. Although central adiposity will be inversely associated with  $VO_{2\text{peak}}$ , we will make sure to carefully select women who have lower central adiposity but are less fit, as well as women with higher central adiposity who have higher levels of activity and are more fit [156-159].

Most women who had estrogen receptor positive breast cancer will be on aromatase inhibitors or tamoxifen. We will collect information about these medications. Some evidence suggests that aromatase inhibitors and tamoxifen may affect cardiovascular risk [160, 161], while other studies did not observe a difference in risk [162] suggesting that this link requires further research at this time [163]. To our knowledge, the effect of these medications on acute cardiovascular changes has not been tested. Accordingly, we will include aromatase inhibitor and tamoxifen use as covariates in secondary analyses to assess whether these medications impact cardiovascular and inflammatory outcomes.

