**Table: Hypothesized group means for negative mood for power calculations**

VACCINE RESPONSE (SD=7.7)			PLACEBO RESPONSE (SD=5.8)			
	Low Depression	High Depression		Low Depression	High Depression	
High Fitness	10	15.2	12.6	High Fitness	8.5	9.1
Low Fitness	11.2	25.2	18.2	Low Fitness	8.7	9.3
Average	10.6	20.2	15.4	Average	8.6	9.2

These means yield effect sizes for the vaccine response of  $d = 0.73$  for the average effect of fitness and  $d = 1.25$  for the average effect of depression. Importantly, in line with Hypothesis 3, they yield an effect size for depression of  $d = 1.8$  for women with low fitness and a smaller effect of  $d = 0.68$  for women with high fitness. Additionally, we will have baseline (pre-injection) measures of outcomes which will be used as covariates in models. In an ongoing study of breast cancer survivors, baseline negative mood was highly correlated with subsequent measures throughout the day, with  $r = 0.79-0.85$ . Inflammatory markers were similarly highly correlated, with correlations of  $r > 0.9$ . To be conservative in the power calculations we assume a single covariate with a correlation of  $r = 0.75$ . **Based on these hypothesized means and one covariate, a sample of size  $n = 180$  will give us 81% power to detect the three-way interaction effect of fitness by depression by injection type on mood. We will also have 94% power for the two-way interaction of depression by injection type and >99% power for the two-way interaction of fitness by injection type.** As previously noted, effects on IL-6 are expected to be larger and group differences should be as big or larger, thus this sample size should provide us the ability to detect the effects on IL-6 as well.

These calculations are conservative for several reasons. As previously noted, our sample is older than the sample on which we base our estimates, thus we will likely see even larger effects and more dramatic effects of age, depression, and fitness and should have higher power. Additionally, power calculations were made assuming fitness and depression were dichotomized; we will obtain continuous measurements of these covariates and thus expect higher power. We will also collect serial measurements of outcomes over time and thus expect to have higher power than if we only obtained a single post-injection measurement.

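### The plan asserts adequate power for the age tests in Aims 2 and 3, but specifies and powers no age effect

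*Combined protocol and SAP*

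**What the plan says.** The Power and Sample Size section treats age and depression as one combined factor. It describes Aim 2 as the two-way interaction of age/depression with injection type and Aim 3 as the three-way interaction that adds fitness. It then says the required sample was based on the "three-way interaction between fitness, age/depression, and injection type, while ensuring adequate power for the first two aims as well". The testing rule is "Throughout we assumed 2-tailed tests with an 0.05 level of significance and used SAS PROC GLMPOWER for calculations", and "our projected sample for the two CRC admissions is 180".

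The groups actually specified are high and low fitness crossed with high and low depression. The table of hypothesized means and the effect sizes beneath it use those two factors. The power statement gives 81% "to detect the three-way interaction effect of fitness by depression by injection type on mood", 94% for depression by injection and above 99% for fitness by injection. It gives no value for age.

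Age is nevertheless a hypothesis in its own right (2a) and part of 2c and 3. In the Data Analysis Plan it replaces fitness in the models for 2a, and under Hypothesis 3 age and depression are tested in separate models. Section B sets the age range: "A total of 240 women ages 45-65". The only figure in the power section that touches age is an assumption that mood responses to both injections "will be 20% higher in our sample of older breast cancer survivors".

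**The concern.** Power computed for depression cannot be carried over to age. Age enters different models, with its own effect size and its own spread, and eligibility limits that spread to 20 years. A reader who meets the combined label age/depression next to a claim of adequate power will assume that both halves were calculated.

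What is at stake is how a null result would be read. A non-significant age-by-injection term from a test described as adequately powered invites the conclusion that age does not alter the response to the vaccine. Without a planned age effect the plan cannot support that reading, and the age conclusions of Aims 2 and 3 would be overstated.

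**Working it through.** **Inputs from the Power and Sample Size section:** n = 180; two-sided 0.05; mood SD 7.7 (vaccine) and 5.8 (placebo); one baseline covariate with r = 0.75; the eight hypothesized means; source-study means 12.8 and 7.4. **Assumed, not in the documents:** equal group sizes, and a residual vaccine-placebo correlation ρ between 0 and 0.75.

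**1. Reproduce the stated 81%.**
- Residual SD = 7.7 × √(1 − 0.75²) = 5.09.
- Three-way contrast = [(25.2 − 11.2) − (15.2 − 10)] − [(9.3 − 8.7) − (9.1 − 8.5)] = 8.8.
- With 180 treated as independent observations over eight cells (22.5 each), SE = 5.09 × √(8/22.5) = 3.04.
- Power is 82.2%; with 22 per cell (176 in all) it is 81.3%. This matches the plan, so I take it as the plan's method.

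**2. Two-way tests by the same method.** SE = 5.09 × √(4/45) = 1.52.
- Depression by injection: (20.2 − 10.6) − (9.2 − 8.6) = 9.0 points; power above 99.9%. The plan prints 94%.
- Fitness by injection: (18.2 − 12.6) − (9.0 − 8.8) = 5.4 points, where 9.0 and 8.8 are the placebo means for low and high fitness; power about 94%. The plan prints above 99%.

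The two printed values appear exchanged. Both exceed 90% either way, so the sample size is unaffected.

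**3. Age contrast needed for 80% power by the plan's method.** The multiplier is 1.96 + 0.84 = 2.80.
- Two-way: 2.80 × 1.52 ≈ 4.25 points, or 4.25/9.0 = 47% of the assumed depression contrast.
- Three-way: 2.80 × 3.04 ≈ 8.5 points.

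**4. The same two-way question in a paired crossover analysis, 90 older and 90 younger women.** SD of the vaccine-placebo difference = 0.661 × √(7.7² + 5.8² − 2ρ × 7.7 × 5.8); SE = that SD × √(2/90).

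| ρ (assumed) | SD of difference | SE | Contrast for 80% power |
|---|---|---|---|
| 0 | 6.38 | 0.95 | 2.7 |
| 0.5 | 4.60 | 0.69 | 1.9 |
| 0.75 | 3.37 | 0.50 | 1.4 |

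**5. Illustration with the 20% uplift.** 12.8 − 7.4 = 5.4; 5.4 × 1.2 = 6.48; gain 1.08 points. If the whole gain were an older-versus-younger contrast within this sample, two-way power would be about 11% by the plan's method. Paired, it would be 20%, 35% and 57% for ρ = 0, 0.5 and 0.75.

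**6. IL-6.** Section A.2 reports that "subjects whose average age was 58 had a 10-fold rise in IL-6 post-vaccination", against a 4-6 fold rise in healthy young subjects of unstated age. I took the log ratio of those rises, spread it over an assumed 25-37 years and scaled it to 10 years. With log-scale SDs derived from the IL-6 means and SDs in the power section, two-way power runs from about 26% to above 99%. The range is too wide to conclude anything.

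**7. Age spread.** If ages were uniform over 45-65, the older and younger halves would average 10 years apart. If the investigators' earlier cohort (mean 55.39, SD 11.26, section A.7.b) were normal and cut to that window, the age SD would fall to about 5.5 and the halves would be a little over 9 years apart.

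**The case against.** The best defence is that the power paragraph labels each value by factor, so a careful reader can see that no age value is offered. The plan also calls its calculation conservative: the sample is older than the source study, larger effects of age are expected, and serial measurements should add power. With a large enough age effect the tests would be well powered: 4.5 points, half the depression contrast, gives 84% two-way power by the plan's method. The Data Analysis Plan also promises emphasis on effect sizes.

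Much of this stands as a limit on the point. A reader might infer that the age tests are underpowered, or that the 20% uplift caps the age effect at about one mood point. The documents support neither. The uplift is a shift between studies, applied to both injections and credited jointly to older age and survivorship. It is not an age slope within 45-65 and is not stated as a maximum. Nor do all planning figures rest on depression: fitness, and hence Aim 1, has its own effect size and power value.

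It does not rescue the claim. That the sample is older than the source study says nothing about how response varies with age inside the sample. The gain expected from continuous measurement is stated for fitness and depression only. The emphasis on effect sizes is aimed at significant but trivial findings, not at null ones.

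**Conclusion.** The plan claims adequate power for Aim 2 and says the sample was sized on the age/depression three-way test, yet no age mean, slope, effect size or power appears anywhere. That rests on the text alone.

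For mood, the age-by-injection test reaches 80% power only for a contrast of about 4.25 points by the plan's method, or about 1.4 to 2.7 points paired. These figures assume equal halves, a single post-injection mood score with the plan's SDs and covariate correlation and, for the paired range, a residual correlation of 0.75 down to 0. The planned area-under-the-curve outcome and continuous age could change them. The 11% and 20-57% values illustrate one generous reading of the uplift and are not estimates of the trial's power.

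Low power for age on inflammation should not be inferred: for IL-6 it is unplanned, not shown to be low.

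**What to change.** In Power and Sample Size, limit the adequate-power statement to fitness and depression. State that no power is claimed for the age part of Aim 2 and of Hypothesis 3, or give the age contrast detectable at n = 180 with its assumptions. When restating the figures, recheck the two-way values against the GLMPOWER output; on recomputation depression by injection is above 99% and fitness by injection about 94%.

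In the Data Analysis Plan, report the age-by-injection and age-by-fitness-by-injection terms as estimates per 10 years with 95% confidence intervals, interpreted within ages 45-65. Add that a non-significant age term will not be taken as evidence of no age effect.

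The cost is wording and a less favourable power statement for age. Sample size, recruitment and models stay as they are.
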